## 11.22.1 DSMC Reviews

DSMC data reviews will be done as follows:

- 1. Formal review of the safety profile data after 7 days following the first vaccination of all 6 participants in Cohort 1. This review will decide on progression to administering the first dose of vaccine to the remaining participants (Cohort 2) in the trial.
- 2. Formal review of the immunological and safety profile including data up to 28 days after the first dose of vaccine has been administered to all participants in Cohort 1 and the first 18

RECRef: 23/SC/0268 NIV001: A study of a new vaccine against Nipah Page 49 of 71 IRAS project ID: 1007433 Virus in adults aged 18 to 55

participants in Cohort 2 (total 24 participants). The trial will continue in parallel to this DSMC review.

- 3. Formal review of the immunological and safety profile including data up to 28 days after the first dose of vaccine has been administered to all participants. The trial will continue in parallel to this DSMC review.
- 4. Formal review of the safety profile data after 7 days following the second vaccination of participants in Cohort 1. This review will decide on progression to administering the second dose of vaccine to the participants in Cohort 2.
- 5. Formal review of the immunological and safety profile including data up to 28 days after the second dose of vaccine has been administered to all participants.
- 6. Independent review following any SAE deemed to be related to the trial active vaccine or placebo.
- 7. Unscheduled reviews on request of the study management committee at a frequency determined by the severity of reported adverse events.

From these reviews the DSMC will make recommendations to the study investigators on whether there are any ethical or safety reasons why the trial should not continue. A summary of all blinded and unblinded AEs and SAEs to date will be provided to the DSMC on request.

The outcome of each DSMC review will be communicated directly to the TMG and documentation of all reviews will be kept in the TMF.

# 11.23 Procedures to be Followed in the Event of Abnormal Findings

Laboratory parameters for inclusion/exclusion in the trial will be considered on an individual basis, with investigator discretion for interpretation of results and the need for repeated tests. Abnormal clinical findings from medical history, examination or blood tests will be assessed as to their clinical significance throughout the trial. If a test result is deemed clinically significant, it may be repeated to ensure it is not a single occurrence or spurious result. If a test remains clinically significant, the participant will be informed and medical care arranged as appropriate and with the permission of the participant. Decisions to exclude the participant from enrolling in the trial or to withdraw a participant from the trial will be at the discretion of the Investigator.

# 11.24 Safety Holding Rules

# 11.24.1 Group Holding Rules

The group holding rules are as follows:

#### • Solicited local adverse events:

o If 2 or more participants (per dose of vaccination) experience the same grade 3 solicited local adverse event beginning within 2 days after vaccination (day of vaccination and one subsequent day) and persisting at grade 3 for >48 hrs.

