#### Solicited systemic adverse events:

o If 2 or more participants (per dose of vaccination) experience the same grade 3 solicited systemic adverse event beginning within 2 days after vaccination (day of vaccination and one subsequent day) and persisting at grade 3 for >48 hrs.

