# • Unsolicited adverse events:

RECRef: 23/SC/0268 NIV001: A study of a new vaccine against Nipah Page 50 of 71

- If 2 or more participants (per dose of vaccination) experience the same grade 3
  unsolicited adverse event (including the same laboratory adverse event, excluding
  lymphopenia) that is considered possibly, probably or definitely related to
  vaccination and persists at grade 3 for >48hrs.
- A serious adverse event considered possibly, probably or definitely related to vaccination occurs.
- o Death occurs.
- o A life-threatening reaction occurs.

If a holding rule has been met, the CI on behalf of the Sponsor will inform the regulatory authority. The DSMC will be asked to review relevant safety data and provide a recommendation on further dosing. If the DSMC recommend to restart dosing, the request (with pertinent data) must be approved by the regulatory authority prior to restarting dosing. The DSMC review would consider:

- The relationship of the AE or SAE to the vaccine.
- The relationship of the AE or SAE to the vaccine dose, or other possible causes of the event.
- If appropriate, additional screening or laboratory testing for other participants to identify those who may develop similar symptoms and alterations to the current Participant Information Sheet (PIS).
- New, relevant safety information from ongoing research programs on the various components of the vaccine.

The vaccine manufacturer (CBF) will also be notified if a holding rule is activated or released. All vaccinated participants will be followed for safety until the end of their planned participation in the study or until resolution or stabilisation (if determined to be chronic sequelae) of their AEs, providing they consent to this.

In addition to these pre-defined criteria, the study can be put on hold upon advice of the DSMC, CI, Study Sponsor, Regulatory Authority or Ethical Committee(s), for any single event or combination of multiple events which they deem jeopardise the safety of the volunteers or the reliability of the data.

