# 11.24.2 Individual Holding Rules

In addition to the above stated group holding rules, holding rules for individual participants will apply (i.e. indications to withdraw individuals from further vaccinations):

- Local reactions: the participant develops injection site ulceration, abscess or necrosis.
- Systemic solicited adverse events: the participant develops a Grade 3 systemic solicited adverse event considered possibly, probably or definitely related to vaccination within 2 days after vaccination (day of vaccination and one subsequent day) and persisting at Grade 3 for >48hrs.
- Laboratory AEs: the participant develops a Grade 3 laboratory adverse event (excluding lymphopenia) considered possibly, probably or definitely related to vaccination within 7 days after vaccination and persisting at Grade 3 for >48hrs (laboratory AE reference ranges are included in Appendix B: Severity Grading Scales).
- Unsolicited adverse events:

RECRef: 23/SC/0268 NIV001: A study of a new vaccine against Nipah Page 51 of 71 IRAS project ID: 1007433 Virus in adults aged 18 to 55

- The participant has a Grade 3 adverse event considered possibly, probably or definitely related to vaccination, persisting continuously at Grade 3 for >48hrs.
- The participant has a serious adverse event considered possibly, probably or definitely related to vaccination.
- The participant has an acute allergic reaction or anaphylactic shock following the administration of an investigational product.

If a participant fulfils any of the temporary exclusion criteria at the scheduled time of a second administration of investigational product, the participant will not receive the vaccine at that time. The vaccine may be administered to that participant at a later date within the time window specified in the protocol or they may be withdrawn from the study at the discretion of the Investigator.

All vaccinated participants will be followed for safety until the end of their planned participation in the study or until resolution or stabilisation (if determined to be chronic sequelae) of their AEs, providing they consent to this.

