# 23 Appendix B: Severity Grading Scales

**Table 9** Severity grading criteria for local adverse events \*erythema ≤2.5cm is an expected consequence of skin puncture and will therefore not be considered an adverse event

Adverse Event	Grade	Intensity
Erythema at injection site*	1	2.5 - 5 cm
	2	5.1 - 10 cm
	3	>10 cm
	4	Necrosis or exfoliative dermatitis

**Table 10** Severity grading criteria for local and systemic AEs. NB: A&E assessment in itself does not constitute a SAE. Refer to 11.1 for SAE definitions.

GRADE 0	None
GRADE 1	Mild: Transient or mild discomfort (< 48 hours); No interference with activity; No medical intervention/therapy required
GRADE 2	Moderate: Mild to moderate limitation in activity – some assistance may be needed; no or minimal medical intervention/therapy required
GRADE 3	Severe: Marked limitation in activity, some assistance usually required; medical intervention/therapy required.
GRADE 4	Potentially Life-threatening: requires assessment in A&E or hospitalisation

Table 11 Severity grading criteria for physical observations (applies to adults only). \*Taken after ≥10 minutes at rest \*\*When resting heart rate is between 60 – 100 beats per minute. Use clinical judgement when characterising bradycardia among some healthy subject populations, for example, conditioned athletes. \*\*\*Only if symptomatic (e.g. dizzy/ light-headed)

Vital Signs	Grade 1 (mild)	Grade 2 (moderate)	Grade 3 (severe)	Grade 4 Potentially Life threatening
Fever (oral)	38.0°C - 38.4°C	38.5°C – 38.9°C	39.0°C - 40°C	> 40°C

RECRef: 23/SC/0268 NIV001: A study of a new vaccine against Nipah Page 67 of 71

Tachycardia (bpm)*	101 - 115	116 – 130	>130	A&E visit or hospitalisation for arrhythmia
Bradycardia (bpm)**	50 – 54	45 – 49	<45	A&E visit or hospitalisation for arrhythmia
Systolic hypertension (mmHg)	141 - 150	151 – 155	≥155	A&E visit or hospitalisation for malignant hypertension
Diastolic hypertension (mmHg)	91 - 95	96 – 100	>100	A&E visit or hospitalisation for malignant hypertension
Systolic hypotension (mmHg)***	85 - 89	80 – 84	<80	A&E visit or hospitalisation for hypotensive shock
Respiratory Rate (breaths per minute)	17 - 20	21-25	>25	Intubation

 Table 12 Oxford Vaccine Group Site Specific Severity Grading Scale for Laboratory AEs

Blood Test	Unit	Grade 1	Grade 2	Grade 3	Grade 4
Albumin	g/L	31 - 28	27 - 25	≤ 24	-
Alkaline phosphate	U/L	143 - 260	261 - 390	391 - 1300	≥ 1301
ALT (female)	U/L	49 - 112	113 - 225	226 - 450	≥ 451

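### The holding rules that count graded events name grade 3 only, so a non-serious grade 4 clinical event, or one that worsens from grade 3 to 4 within 48 hours, does not count

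*Protocol*

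**What the plan says.** Section 11.24.1 has three group rules that count graded events.

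- **Solicited local:** a hold "If 2 or more participants (per dose of vaccination) experience the same grade 3 solicited local adverse event beginning within 2 days after vaccination", with the event remaining at grade 3 for more than 48 hours.
- **Solicited systemic:** the same construction, for two or more participants who "experience the same grade 3 solicited systemic adverse event".
- **Unsolicited, including laboratory:** the same related grade 3 event in two or more participants that "persists at grade 3 for >48hrs".

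Section 11.24.2 repeats the pattern for individuals. Further doses stop if "the participant develops a Grade 3 systemic solicited adverse event" (related, early onset, more than 48 hours at grade 3), or for a related grade 3 unsolicited event "persisting continuously at Grade 3 for >48hrs". A similar rule covers laboratory events.

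Appendix B has a distinct grade 4. For symptoms, Table 10 defines it as "Potentially Life-threatening: requires assessment in A&E or hospitalisation". For fever, Table 11 sets it above 40°C, with grade 3 running from 39.0 to 40°C.

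Other triggers need only one event. The group is held if "A serious adverse event considered possibly, probably or definitely related to vaccination occurs", on any death, or on a life-threatening reaction. Section 11.12 makes every grade 4 laboratory event an SAE. Section 11.24.1 also allows a discretionary hold.

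**The concern.** A severity threshold in a stopping rule should be monotone: a worse event should count at least as much as a milder one. Here the named grade is also the ceiling, in both the entry condition and the persistence condition. Other triggers catch a grade 4 event only if it is also judged serious or life-threatening, and the protocol says twice that an A&E visit does not by itself make an event serious. It closes this gap for laboratory values but has no matching sentence for clinical events.

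What is at stake is the mandatory pathway. Once a holding rule is met, the regulator is informed, the DSMC reviews, and dosing restarts only with regulatory approval. Two persistent grade 3 events oblige all of that; two non-serious grade 4 events do not. The discretionary hold could be used, but the text does not attach that pathway to it.

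Under section 11.7 participants grade most solicited symptoms themselves, so whether an event counts can turn on a participant entering 4 rather than 3.

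**Working it through.** No stated figure in the protocol depends on this point. The check is a comparison of texts, two worked examples and an illustration under assumed rates.

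**1. Triggers that count graded events (11.24.1 and 11.24.2)**

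| Trigger | Grade named | Persistence required | Non-serious grade 4 clinical event counted? |
|---|---|---|---|
| Group, solicited local | 3 | at grade 3, >48 h | No |
| Group, solicited systemic | 3 | at grade 3, >48 h | No |
| Group, unsolicited | 3 | at grade 3, >48 h | No (laboratory grade 4 is covered by 11.12) |
| Individual, systemic solicited | 3 | at grade 3, >48 h | No |
| Individual, laboratory | 3 | at grade 3, >48 h | Not applicable; grade 4 is an SAE under 11.12 |
| Individual, unsolicited | 3 | continuously at grade 3, >48 h | No |

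Affected: 3 of 3 group rules plus 2 of 3 individual rules = 5 of 6.

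**2. Solicited events that can be grade 4 without being an SAE**

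Table 7 lists 5 local + 9 systemic = 14 events. Redness and fever are measured, leaving 14 − 2 = 12 graded on Table 10, where A&E assessment alone reaches grade 4. Adding fever (grade 4 above 40°C) gives 12 + 1 = 13 of 14. Redness is left out because its grade 4 includes necrosis, which has its own individual trigger.

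**3. Worked examples** (onset within the required window, same dose, not judged serious or life-threatening)

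- Two participants at 39.5°C for 49 h: grade 3, 49 > 48, count = 2, hold.
- The same two at 40.2°C for 49 h: grade 4, count = 0, no hold under the counting rules.
- Fever at 39.5°C for 30 h, then 40.2°C for 19 h: 30 + 19 = 49 h at grade 3 or above, but only 30 h at grade 3. This fails the >48 h condition and contributes 0.

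**4. Wording elsewhere**

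The eDiary footnotes to Tables 2 and 3 use grade ≥3, section 11.9.2 uses grade 3 or 4, and section 11.12 uses grade 2 or above. The protocol therefore has wording for a minimum grade and does not use it in 11.24. Section 9.5 says only grade 3 for an email alert that 11.9.2 describes as grade 3 or 4.

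**5. Effect on the chance of a hold (illustration only)**

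The protocol gives no rates, so these are assumptions. Let p3 be the probability that a participant has a given qualifying event that stays at grade 3, and p4 the probability of the same event at non-serious grade 4. With independent participants,

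P(at least 2) = 1 − (1 − p)^n − n·p·(1 − p)^(n−1),

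with p = p3 as worded and p = p3 + p4 as corrected. Active recipients number n = 6 + 20 + 20 = 46 at the first dose and n = 6 + 20 = 26 at the second.

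| n | p3 | p4 | Grade 3 only | Grade 3 or above |
|---|---|---|---|---|
| 46 | 2% | 0.5% to 1% | 0.235 | 0.320 to 0.403 |
| 46 | 5% | 1% to 2% | 0.677 | 0.771 to 0.842 |
| 46 | 0 | 2% to 5% | 0 | 0.235 to 0.677 |
| 26 | 2% | 0.5% to 1% | 0.095 | 0.137 to 0.183 |
| 26 | 5% | 1% to 2% | 0.376 | 0.468 to 0.552 |

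The n = 46, p3 = 0 row shows the structural point: if every qualifying event is a non-serious grade 4, the rule as worded can never trigger.

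**The case against.** The strongest reply is that the life-threatening-reaction trigger is meant to take up grade 4. It is listed separately from the related-SAE trigger, would add little if it meant only actual risk of death, and Appendix B labels grade 4 potentially life-threatening. The note in 11.1 defines the term only for seriousness. This is possible, but 11.24 does not say it, and the only definition in the protocol requires that the participant was actually at risk of death.

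Second, the residual gap is small. The event must be grade 4 without admission, not an important medical event and not life-threatening. To change the group outcome it must also be the same event in two participants after the same dose. This stands, and it limits the severity of the point. The counts of 5 of 6 and 13 of 14 describe categories, not risk.

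Third, other safeguards exist: deferral of vaccination (8.2), investigator or DSMC discontinuation (9.7), regular blinded safety review (11.19) and DSMC reviews before key dosing steps (11.22.1). Near-real-time monitoring at grade ≥3 means such events would be seen. These are mainly discretionary or scheduled, and none carries the mandatory regulator-approval pathway.

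Fourth, staff would probably read grade 3 as a minimum. That is likely, but a mandatory rule should not depend on it.

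Finally, the planned period (Q3 2023 to Q4 2024, with 12 months of follow-up) suggests that dosing may have finished before version 4.0 of 16 August 2024. Actual dosing dates are not shown. If dosing is complete, the change no longer affects this trial's holds and matters only where the wording is reused.

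**Conclusion.** The concern holds: as written, the grade-counting rules miss non-serious grade 4 clinical events and events that move from grade 3 to grade 4 within 48 hours. Five of six grade-counting triggers and 13 of 14 solicited events are exposed. The conclusion rests on a literal reading and on the event being judged neither serious nor life-threatening. Related SAEs, deaths, grade 4 laboratory events judged related, injection-site necrosis (for the individual) and acute allergic reactions (for the individual) are already covered. No frequency is claimed. The gap is narrow, but it lies in a pre-defined safety rule of a first-in-human trial and should be corrected.

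**What to change.** In 11.24.1 and 11.24.2, replace grade 3 with *grade 3 or above* wherever it defines a trigger, and make the persistence condition *at grade 3 or above* in all its variants. Align the alert in 9.5 with 11.9.2; that edit is clerical.

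The cost is a short wording amendment, plus a matching line in the DSMC charter if it repeats the rule. No extra data or participants are needed. The one operating consequence is a higher chance of a hold. It is small if non-serious grade 4 events are rare and larger at the assumed rates above, and the added holds come only from events at least as severe as those the rule already counts.

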#### Solicited systemic adverse events:

o If 2 or more participants (per dose of vaccination) experience the same grade 3 solicited systemic adverse event beginning within 2 days after vaccination (day of vaccination and one subsequent day) and persisting at grade 3 for >48 hrs.

# • Unsolicited adverse events:

RECRef: 23/SC/0268 NIV001: A study of a new vaccine against Nipah Page 50 of 71

- If 2 or more participants (per dose of vaccination) experience the same grade 3
  unsolicited adverse event (including the same laboratory adverse event, excluding
  lymphopenia) that is considered possibly, probably or definitely related to
  vaccination and persists at grade 3 for >48hrs.
- A serious adverse event considered possibly, probably or definitely related to vaccination occurs.
- o Death occurs.
- o A life-threatening reaction occurs.

If a holding rule has been met, the CI on behalf of the Sponsor will inform the regulatory authority. The DSMC will be asked to review relevant safety data and provide a recommendation on further dosing. If the DSMC recommend to restart dosing, the request (with pertinent data) must be approved by the regulatory authority prior to restarting dosing. The DSMC review would consider:

- The relationship of the AE or SAE to the vaccine.
- The relationship of the AE or SAE to the vaccine dose, or other possible causes of the event.
- If appropriate, additional screening or laboratory testing for other participants to identify those who may develop similar symptoms and alterations to the current Participant Information Sheet (PIS).
- New, relevant safety information from ongoing research programs on the various components of the vaccine.

The vaccine manufacturer (CBF) will also be notified if a holding rule is activated or released. All vaccinated participants will be followed for safety until the end of their planned participation in the study or until resolution or stabilisation (if determined to be chronic sequelae) of their AEs, providing they consent to this.

In addition to these pre-defined criteria, the study can be put on hold upon advice of the DSMC, CI, Study Sponsor, Regulatory Authority or Ethical Committee(s), for any single event or combination of multiple events which they deem jeopardise the safety of the volunteers or the reliability of the data.

# 11.24.2 Individual Holding Rules

In addition to the above stated group holding rules, holding rules for individual participants will apply (i.e. indications to withdraw individuals from further vaccinations):

- Local reactions: the participant develops injection site ulceration, abscess or necrosis.
- Systemic solicited adverse events: the participant develops a Grade 3 systemic solicited adverse event considered possibly, probably or definitely related to vaccination within 2 days after vaccination (day of vaccination and one subsequent day) and persisting at Grade 3 for >48hrs.
- Laboratory AEs: the participant develops a Grade 3 laboratory adverse event (excluding lymphopenia) considered possibly, probably or definitely related to vaccination within 7 days after vaccination and persisting at Grade 3 for >48hrs (laboratory AE reference ranges are included in Appendix B: Severity Grading Scales).
- Unsolicited adverse events:

RECRef: 23/SC/0268 NIV001: A study of a new vaccine against Nipah Page 51 of 71 IRAS project ID: 1007433 Virus in adults aged 18 to 55

- The participant has a Grade 3 adverse event considered possibly, probably or definitely related to vaccination, persisting continuously at Grade 3 for >48hrs.
- The participant has a serious adverse event considered possibly, probably or definitely related to vaccination.
- The participant has an acute allergic reaction or anaphylactic shock following the administration of an investigational product.

If a participant fulfils any of the temporary exclusion criteria at the scheduled time of a second administration of investigational product, the participant will not receive the vaccine at that time. The vaccine may be administered to that participant at a later date within the time window specified in the protocol or they may be withdrawn from the study at the discretion of the Investigator.

All vaccinated participants will be followed for safety until the end of their planned participation in the study or until resolution or stabilisation (if determined to be chronic sequelae) of their AEs, providing they consent to this.

#### 12 DATA MANAGEMENT

The data management aspects of the study are summarised here with details fully described in the Data Management Plan.

The Investigators will populate the content of the participants' CRFs, which will be in a paper and/or electronic format (eCRF) using a REDCap database. The database will be stored on a secure University of Oxford server and will have restricted access (password-protection) and accountability records. These data include safety data, laboratory data (both clinical and immunological) and outcome data. All information transcribed to and from the database will be done by encrypted (Https) transfer.

Each study participant will have a unique participant number which will be allocated at the time a screening visit is booked. Names and/or identifying details are not included in any study data electronic file, with the exception of the electronic diaries, for which consent will be obtained to store the participant email address, which is necessary for the system to function. Only site research staff and sponsor data managers have access to view the email address. After enrolment the participants will be identified by a study specific participant number and/or code. With the exception of clinical safety blood samples, which are sent to local clinical laboratories and follow local sample labelling requirements, samples sent to laboratories for processing will be identified by trial number and participant number only.

